TITLE PAGE

Division: Worldwide Development

Information Type: Worldwide Epidemiology Study Protocol

Title:	A prospective observational cohort study nested within the Hepatitis C Therapeutic Registry and Research Network (HCV-TARGET) to evaluate real world use of eltrombopag in adult patients with chronic hepatitis C virus infection who are unable to initiate or maintain optimal interferon-based therapy due to thrombocytopenia.
---------------	---

Compound Number: SB-497115

Development Phase IV

Effective Date: 12-AUG-2014

Subject: Hepatitis C Virus, Thrombocytopenia, Cohort study

Author(s): [REDACTED]

PASS information

Title	A prospective observational cohort study nested within the Hepatitis C Therapeutic Registry and Research Network (HCV-TARGET) to evaluate real world use of eltrombopag in adult patients with chronic hepatitis C virus infection who are unable to initiate or maintain optimal interferon-based therapy due to thrombocytopenia.
Protocol version identifier	02
Date of last version of protocol	20-MAR-2014
EU PAS register number	To be registered after PRAC approval
Active substance	Eltrombopag
Medicinal product	Eltrombopag
Product reference	SB-497115-GR
Procedure number	Not applicable
Marketing authorisation holder(s)	GlaxoSmithKline Trading Services Limited [name] Country: Ireland Telephone: [REDACTED]
Joint PASS	No
Research question and objectives	The primary objective of this study is to report the incidence of hepatic decompensation in a real-world setting in patients with chronic hepatitis C virus infection who receive eltrombopag therapy with interferon-based therapy that also includes direct acting anti-viral agents, a group not studied in the Phase III randomized clinical trials. Secondary objectives include reporting the real-world incidence of thromboembolic events and mortality and identifying risk factors for hepatic decompensation, thromboembolic events and mortality in this group of understudied patients. The study will also report the 3-year incidence of hepatic decompensation and mortality, comparing patients who achieve sustained

1. LIST OF ABBREVIATIONS

AE	Adverse Event
EMA	European Medicines Agency
ENABLE 1	Eltrombopag to INitiate and Maintain Interferon Antiviral Treatment to Benefit Subjects with Hepatitis C related Liver Disease
ENABLE 2	Eltrombopag to INitiate and Maintain Interferon Antiviral Treatment to Benefit Subjects with Hepatitis C related Liver Disease
GSK	GlaxoSmithKline
HCV	Hepatitis C Virus
HCV-TARGET	Hepatitis C Therapeutic Registry and Research Network
IFN	Interferon
DAA	Direct acting anti-virals
SAE	Serious adverse event
EVR	Early virologic response
SVR	Sustained virologic response
PI	Principal Investigator
RNA	Ribonucleic acid
TCP	Thrombocytopenia

Trademark Information

Trademarks of the GlaxoSmithKline group of companies
PROMACTA / REVOLADE

Trademarks not owned by the GlaxoSmithKline group of companies
SAS

3. ABSTRACT

***Title** A prospective observational cohort study nested within the Hepatitis C Therapeutic Registry and Research Network (HCV-TARGET) to evaluate real world use of eltrombopag in adult patients with chronic hepatitis C virus infection who are unable to initiate or maintain optimal interferon-based therapy due to thrombocytopenia.

***Rationale and background.** Hepatitis C Virus (HCV) is a leading cause of chronic liver disease worldwide. Treatment consists of combination therapy with peginterferon and ribavirin (double therapy) or where appropriate, interferon, ribavirin and a direct acting anti-viral agent (triple therapy), although the treatment landscape is changing rapidly with new therapies. Thrombocytopenia as an interferon-related adverse event or a complication of chronic liver disease often necessitates dose reduction and discontinuation of interferon-based therapy in these patients.

Eltrombopag (Revolade™/Promacta™) is an oral second generation thrombopoietin receptor agonist which promotes megakaryocyte differentiation and proliferation. Eltrombopag (Promacta) was approved in the U.S. in November 2012 for chronic hepatitis C virus (HCV)-associated thrombocytopenia to allow for the initiation and maintenance of interferon-based therapy. Eltrombopag (REVOLADE) was approved by the European Commission in September 2013 for the treatment of thrombocytopenia in adult patients with HCV, where the degree of thrombocytopenia is the main factor preventing the initiation or limiting the ability to maintain optimal interferon-based therapy. Eltrombopag allows patients who would otherwise have been poor candidates due to low platelet counts to undergo interferon-based therapy for HCV.

In the randomized clinical trials program, there was an increased incidence of hepatic decompensation events that occurred in the eltrombopag arm vs. the placebo arm (10% vs 5%, respectively), an increased incidence of thromboembolic events (3% vs 1%), and a higher death event (3% vs 2%). The incidence of hepatic decompensation and thromboembolic events has been adequately assessed in previous randomized double-blinded placebo controlled clinical trials that included more than 1,500 patients and the current label for eltrombopag contains a warning for hepatotoxicity and hepatic decompensation. However, the occurrence of hepatic decompensation and other adverse events have not been characterized in thrombocytopenic HCV patients who have received direct acting agents in combination with interferon-based therapy.

GSK will take a proactive pharmacovigilance approach in generating incidence of hepatic decompensation and other events through long-term follow-up of eltrombopag users in eltrombopag HCV patients undergoing interferon-based anti-HCV treatment with direct acting agents. Results will be reported to the EMA and the FDA and other regulatory agencies. Information will be made available publically through the Clinical Trial Registry and, if approved by the HCV-

TARGET Publication Committee, results will be published in one or more peer-reviewed journal publications.

***Research question and Objective(s).** The primary objective of this study is to report the incidence of hepatic decompensation in patients with chronic hepatitis C virus infection who receive eltrombopag therapy with interferon-based therapy that also includes direct acting anti-viral agents, a group not studied in the Phase III randomized clinical trials. Secondary objectives include reporting the real-world incidence of thromboembolic events and mortality and identifying risk factors for hepatic decompensation, thromboembolic events and mortality in this group of understudied patients. The study will also report the 3-year incidence of hepatic decompensation and mortality, comparing patients who achieve sustained virologic response to patients who do not achieve SVR among eltrombopag patients treated with interferon-based therapy and direct acting agents, which has not yet been studied. The study will also examine effectiveness of eltrombopag to initiate and maintain HCV therapy and achieve EVR and SVR among patients specifically using direct-acting anti-virals with interferon-based therapy.

***Study Design.** The study is nested within the on-going Hepatitis C Therapeutic Registry and Research Network. The HCV-TARGET study is a carefully maintained longitudinal observational research registry to prospectively enrol and follow HCV patients treated with anti-HCV regimens in a real-world setting in order to rapidly inform strategies for better management of populations underrepresented in clinical trials, identify and remediate gaps in treatment guidelines and adverse event management in order to optimize rates of SVR. It is comprised of patients that receive HCV therapy with direct acting antiviral agents. The planned enrolment is 5000 patients. The GSK study nested with the HCV-TARGET study will comprise all patients treated with eltrombopag. Patients will be followed for up to three years after eltrombopag initiation.

***Population.** All patients treated with eltrombopag who are participants of the HCV-TARGET will be included in the GSK study nested. Most patients will receive direct-acting antivirals as part of their HCV therapy.

***Variables.** Outcome variables include: hepatic decompensation, thromboembolic events, overall and cause-specific mortality, ability to initiate interferon-based antiviral therapy, ability to maintain interferon-based antiviral therapy, and ability to reach early and sustained virologic response. The main exposure variables include treatment with eltrombopag, peginterferon, ribavirin, direct acting anti-viral agents, and other antiviral therapy.

***Data sources.** Within HCV-TARGET, patients are enrolled prospectively at participating sites and treated per local standard of care. Source data is the original medical record. All original clinic notes, telephone notes, safety and efficacy labs collected during the treatment observation period are submitted to a central data repository. Patient data from submitted records is abstracted at the HCV-TARGET clinical coordinating center and entered into the registry database. Where possible, data can be mapped directly from electronic medical records for transfer into the registry database.

***Study size.** Of the 2707 patients enrolled to date into HCV-TARGET with data available on concomitant medications, 58 patients received eltrombopag (2.1%). Based on the enrolment rate of 2.1%, it is estimated that 105 eltrombopag patients will comprise the nested HCV-TARGET cohort study. Almost all of these patients will be taking direct acting antivirals.

***Data analysis**

Cumulative incidence rates and corresponding 95% confidence intervals as well as Kaplan-Meier rates and corresponding 95% confidence intervals will be calculated for the occurrence of hepatic decompensation, thromboembolic events, or mortality, as separate events, at multiple time points during and at the end of the 3-year follow-up period. Baseline factors potentially predictive of events will be identified through Kaplan-Meier survival estimates for patients with vs. without the factor and testing for statistical significance using the log-rank test. Cox proportional hazards models will be constructed to evaluate the influence of these identified factors simultaneously.

Patient demographics and characteristics will be described at the time of initiation of eltrombopag. Virology, laboratory information, information on dose and duration of eltrombopag, early and sustained virologic response, anti-viral therapy and incidence of hepatic decompensation and thromboembolic events will be described at baseline and distinct follow-up time points. Continuous variables will be reported as mean, standard deviation, median, 25th and 75th quartiles, and range. Categorical variables will be summarized as number and proportion of subjects with observed (non-missing) data, with corresponding 95% confidence intervals (CI) by exact methods.

The number and percentage of patients who achieve early virologic response and sustained virologic response will be reported at distinct follow-up time points. The probability of attaining EVR and SVR by these time points will be presented as Kaplan-Meier estimates, along with median time to attaining virologic response.

***Milestones.** An interim analysis will be conducted in 2016 and the final analysis will be completed in 2018.

4. AMENDMENTS AND UPDATES

None.

5. MILESTONES

Milestone	Planned date
Start of data collection	TBD, after protocol approval
End of data collection	2018
Interim report 1	March 2016
Registration in the EU PAS register	TBD, after protocol approval
Generate tables for final analysis	March 2018
Final report of study results	2018

6. RATIONALE AND BACKGROUND

6.1. Background

Hepatitis C Virus (HCV) is a leading cause of chronic liver disease worldwide. Treatment consists of combination therapy with peginterferon and ribavirin (double therapy) or interferon, ribavirin and a direct acting anti-viral agent (triple therapy). Thrombocytopenia as a treatment related adverse event or a complication of chronic liver disease often necessitates dose reduction and discontinuation in these patients.

Eltrombopag (Revolade/Promacta) is an oral second generation thrombopoietin receptor agonist which promotes megakaryocyte differentiation and proliferation. Two global, randomized, double-blinded Phase III trials evaluated the efficacy of eltrombopag in 1500 HCV patients with platelet counts of less than 75,000 using a primary endpoint of achieving sustained viral response. In ENABLE 1, 23% of the eltrombopag group achieved a sustained virologic response versus 14% of the placebo group ($P=0.0064$). In ENABLE 2, 19% of the eltrombopag group achieved SVR versus 13% of the placebo group ($p=0.0202$) (Afdhal, 2014).

Eltrombopag (Promacta) was approved in the U.S. in November 2012 for chronic hepatitis C virus (HCV)-associated thrombocytopenia to allow for the initiation and maintenance of interferon-based therapy. Eltrombopag (Revolade) was approved by the European Commission in September 2013 with indication as follows: *Revolade is indicated in adult patients with chronic hepatitis C virus (HCV) infection for the treatment of thrombocytopenia, where the degree of thrombocytopenia is the main factor preventing the initiation or limiting the ability to maintain optimal interferon-based therapy.*

Eltrombopag allows patients who would otherwise have been poor candidates due to low platelet counts to undergo interferon-based therapy for HCV.

6.2. Rationale

In the randomized clinical trials program, there was an increased incidence of hepatic decompensation events that occurred in the eltrombopag arm vs. the placebo arm (10% vs 5%, respectively), an increased incidence of thromboembolic events (3% vs 1%), and a higher death event (3% vs 2%) (Afdhal, 2014). The incidence of hepatic decompensation and thromboembolic events have been adequately assessed in previous randomized double-blinded placebo controlled clinical trials that included more than 1,500 patients and the current label for eltrombopag contains a warning for hepatotoxicity and hepatic decompensation. However, the occurrence of hepatic decompensation and other adverse events has not been characterized in thrombocytopenic HCV patients who have received direct acting agents in combination with interferon-based therapy.

GSK will take a proactive pharmacovigilance approach in generating incidence of hepatic decompensation and other events through long-term follow-up of eltrombopag users in eltrombopag HCV patients undergoing interferon-based anti-HCV treatment with direct acting agents. Results will be reported to the EMA and the FDA and other regulatory agencies. Information will be made available publically through the Clinical Trial

Registry and, if approved by the HCV-TARGET Publication Committee, results will be published in one or more peer-reviewed journal publications.

7. RESEARCH QUESTION AND OBJECTIVE(S)

The primary objective of this study is to report the incidence of hepatic decompensation in patients with chronic hepatitis C virus infection who receive eltrombopag therapy with interferon-based therapy that also includes direct acting anti-viral agents, a group not studied in the Phase III randomized clinical trials. Secondary objectives include reporting the real-world incidence of thromboembolic events and mortality and identifying risk factors for hepatic decompensation, thromboembolic events and mortality in this group of understudied patients. The study will also report the 3-year incidence of hepatic decompensation and mortality, comparing patients who achieve sustained virologic response to patients who do not achieve SVR among eltrombopag patients treated with interferon-based therapy and direct acting agents, which has not yet been studied. The study will also examine effectiveness of eltrombopag to initiate and maintain HCV therapy and achieve EVR and SVR among patients specifically using direct-acting anti-virals with interferon-based therapy.

Specific Study Aims

- Primary: Determine the incidence of hepatic decompensation among patients receiving eltrombopag with interferon-based therapy and direct acting anti-viral agents,
Secondary:
- Determine the incidence of thromboembolic events and mortality among patients receiving eltrombopag with interferon-based therapy and direct acting anti-viral agents
 - Explore factors associated with risk of hepatic decompensation and risk of thromboembolic events among patients receiving eltrombopag with interferon-based therapy and direct acting anti-viral agents
 - Determine the incidence rate ratio of hepatic decompensation and mortality at 3 years, comparing eltrombopag patients achieving sustained virologic response to eltrombopag patients who did not achieve SVR in the setting of treatment with interferon-based therapy and direct acting anti-viral agents
 - Obtain information on treatment effectiveness among patients receiving eltrombopag with interferon-based therapy and direct acting anti-virals with respect to initiating, maintaining and completing HCV therapy, and achieving EVR and SVR

8. RESEARCH METHODS

8.1. Study Design

The HCV-TARGET study is a carefully maintained longitudinal observational research registry to prospectively enrol and follow HCV patients treated with anti-HCV regimens in a real-world setting in order to rapidly inform strategies for better management of populations underrepresented in clinical trials, identify and remediate gaps in treatment

guidelines and adverse event management in order to optimize rates of SVR. It's comprised of patients that receive HCV therapy with direct acting antiviral agents. All adult patients (age 18 or older) who are prescribed HCV treatment with direct acting antiviral agents outside of a clinical trial are eligible for participation, provided they provide written informed consent and are not participating in any other registry or study where HCV treatment outcomes are reported, except where approved or conducted as an adjunct project of the HCV-TARGET registry.

This study is an eltrombopag cohort study nested within HCV-TARGET, comprising all patients treated with eltrombopag. Nesting the eltrombopag cohort study within the HCV-TARGET is an efficient way to identify and study eltrombopag users in a real-world setting. All patients treated with eltrombopag will be included in the nested cohort study. No patients who have not been exposed to eltrombopag will be included in the nested cohort study. Within the nested cohort study, patients will be followed for up to three years after eltrombopag initiation. The major safety outcome is hepatic decompensation. Incidence of thromboembolic events and mortality will also be determined. Thromboembolic events include myocardial infarction, ischemic stroke, pulmonary embolism, deep vein thrombosis, portal vein thrombosis, and other events. The major effectiveness outcomes include ability to initiate anti-viral therapy, ability to maintain anti-viral therapy, early virologic response and sustained virologic response. The incidence of hepatic decompensation and of mortality at three years will be compared between eltrombopag users who achieve SVR and those users who do not achieve SVR. An interim analysis will be conducted in 2016 and the final analysis will be completed in 2018.

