8.3.2. Exposure

- The main exposure variable is Treatment with eltrombopag, including dose, duration of treatment, drug discontinuation, In combination with peginterferon, ribavirin, and direct acting antiviral agents (triple therapy)

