8.9. Strengths and limitations of the research methods

A strength of this study is that it will report the incidence of hepatic decompensation and other events among eltrombopag-users in the group of HCV patients receiving direct acting anti-viral agents as part of their interferon-based therapy, a group that was not part of the randomized clinical trial program because DAAs were not available at the time of RCT start. Very little information is available for this group of patients. HCV-TARGET is comprised almost entirely of patients receiving DAAs. A second strength is that selection bias will be minimized because all patients in HCV-TARGET who receive

eltrombopag will be included in the nested cohort study. Thirdly, there are multiple centers (over 103) participating in the study to provide patient diversity. . A fourth strength is that information on outcomes, exposures and covariates are abstracted directly from the medical record, ensuring high detection rates for major events.

A major limitation of the study is the small sample size. Because of the small sample size and the low event rates of interest, it is not feasible to implement a study design that successfully uses a control group of non-eltrombopag users upon which to test if rates are higher than expected. For the event of hepatic decompensation, its estimated that power to detect differences comparing eltrombopag users to non-users would be only 19% if propensity score matching is performed on a 1:1 bases and 44% if matching is on a 1:6 basis, based on the projected number of eltrombopag users.

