9. PROTECTION OF HUMAN SUBJECTS

9.1. Ethical approval and subject consent

The HCV-TARGET protocol and informed consent documents received approval by the local site IRB prior to initiation of the study at each site. Consent for participation in HCV-TARGET includes permission 1) to submit de-identified historical medical records related to patient demographics, medical/co-morbid condition history, prior HCV therapy and evaluation of liver disease, 2) to submit prospective de-identified medical records related to HCV treatment response, safety, side effects, side effect management and safety/efficacy outcomes of antiviral therapy; 3) for collection of biospecimens including genomic DNA to be archived for future studies (optional); and 4) to be followed for HCV co-morbid conditions and mortality for up to 3 years after treatment outcome is determined.

Written informed consent must be obtained before any data collection and may be given by patients after being prescribed HCV treatment up to 4 weeks after treatment initiation. The method of obtaining and documenting the informed consent and the contents of the consent complies with ICH GCP guidelines and all applicable laws and regulations.

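### The cohort rule is wider than the primary objective, and follow-up starts at eltrombopag initiation although some patients can enter only at a later consent, so early incidence is biased low by an unknown amount

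*Protocol*

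**What the plan says.** **Who is in the cohort.** Section 8.1: "All patients treated with eltrombopag will be included in the nested cohort study". The parent registry's entry rule, in the same section, is a DAA prescription: "All adult patients (age 18 or older) who are prescribed HCV treatment with direct acting antiviral agents outside of a clinical trial are eligible". Interferon is not mentioned as a condition.

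**Whom the estimate is for.** Section 7: "Primary: Determine the incidence of hepatic decompensation among patients receiving eltrombopag with interferon-based therapy and direct acting anti-viral agents". Section 8.3.2 defines the main exposure as eltrombopag "In combination with peginterferon, ribavirin, and direct acting antiviral agents (triple therapy". The opening of Section 8.7 describes the same interferon-plus-DAA group.

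**How many are on the target regimen.** The Population paragraph of the abstract says "Most patients will receive direct-acting antivirals as part of their HCV therapy". The Study size paragraph of the abstract and Section 8.5 put it more strongly, at almost all, and Section 8.9 says the registry consists almost entirely of DAA patients. No share is given for interferon.

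**When the clock starts and when a patient can enter.** Section 8.1 follows patients for up to three years from eltrombopag initiation. Section 9.1 requires written consent before any data collection, and consent "may be given by patients after being prescribed HCV treatment up to 4 weeks after treatment initiation". It also lets consenting patients' historical records be submitted.

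**What is said about selection.** Section 8.9 claims that "selection bias will be minimized because all patients in HCV-TARGET who receive" eltrombopag are included.

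**The concern.** Two things do not line up.

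First, the inclusion rule admits any eltrombopag user in the registry, while the aims, the exposure and the analysis preamble describe users on interferon plus a DAA. If the primary incidence is computed on everyone included, it may mix regimens with different risks. It would then not describe the group that the protocol says was never studied in the phase III trials.

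Second, eltrombopag is given partly so that antiviral therapy can begin, so some patients start it before they can be enrolled. With eltrombopag start as time zero and no entry time, the analysis counts weeks in which a patient had to survive and remain a treatment candidate in order to be seen at all. Sections 8.7 and 8.9 deal with censoring and with completeness inside the registry, but not with this. In a safety study requested by a regulator, the bias runs in the reassuring direction. The percentage of users able to initiate antiviral therapy (Section 8.3.1) is affected too. Registry entry already requires an HCV prescription, so users who never got that far are missing from the denominator and the percentage is biased high.

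**Working it through.** **1. The plan's own figures.** Section 8.5 projects 2.1% × 5000 = 105 patients, which reproduces. Its half-widths at a 10% event rate are 0.083, 0.058, 0.047 and 0.041 for n = 50, 100, 150 and 200. The plain formula 1.96 × √(0.10 × 0.90 / n) gives 0.0832, 0.0588, 0.0480 and 0.0416. Multiplying by √(1 − n/5000) gives 0.0827, 0.0582, 0.0473 and 0.0407, which matches all four. These figures are sound as arithmetic, but n counts every eltrombopag user. None is for the interferon-plus-DAA group.

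**2. Precision if the primary set is restricted.** The target share f is not in the protocol, so it is varied as an assumption. With n = f × 105 and the plain formula:

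| f (assumed) | n | half-width at 10% |
|---|---|---|
| 1.00 | 105 | 0.057 |
| 0.90 | 94 | 0.061 |
| 0.75 | 79 | 0.066 |
| 0.50 | 52 | 0.082 |

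**3. Mixing if it is not restricted.** Pooled risk = f × 10% + (1 − f) × r, where r is the assumed risk off the target regimen. With r = 5% or 15%, f = 0.90 gives 9.5% or 10.5%, and f = 0.50 gives 7.5% or 12.5%. The direction is not known in advance.

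**4. Late entry.** The 10% risk is the planning value in Section 8.5. Assumptions: the hazard h is constant over T weeks, there is a gap of L weeks from eltrombopag start to entry, and every patient with an event before entry is lost.

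- h = −ln(0.9)/T
- events before entry: m = 1 − exp(−hL)
- apparent risk among those who enter: (0.10 − m)/(1 − m)

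| Risk accrues over | L (weeks) | m | apparent risk |
|---|---|---|---|
| T = 156 weeks | 4 | 0.27% | 9.8% |
| | 8 | 0.54% | 9.5% |
| | 13 | 0.87% | 9.2% |
| T = 48 weeks | 4 | 0.87% | 9.2% |
| | 8 | 1.74% | 8.4% |
| | 13 | 2.81% | 7.4% |

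For a given gap and hazard these are the largest effects, because they assume that every patient has the gap and that no earlier event is recovered.

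**5. Does the analysis section already correct for it?** Section 8.7 specifies cumulative incidence, Kaplan-Meier, log-rank and Cox analyses, and uses data up to last contact for patients lost to follow-up. That handles the end of follow-up. Nothing there handles a late start.

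**The case against.** **The exposure definition and the analysis preamble already imply the restriction, and an analysis set can be left to the SAP.** This stands in part: Sections 7, 8.3.2 and 8.7 agree with one another. But Section 8.1 states a wider rule outright, and Section 8.5 sizes the study on it. That is a conflict within the protocol, not merely a detail deferred.

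**Nearly all patients will be on DAAs, and the indication ties eltrombopag to interferon.** This is fair. A reader who takes only the Population paragraph of the abstract might infer that a sizeable part of the cohort is off DAAs. Sections 8.1, 8.5 and 8.9 do not support that. The open question is interferon, for which no share is stated.

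**The wide inclusion rule has a purpose.** Initiation of antiviral therapy cannot be studied only in those who received it. This is correct, and it is why all users should stay as a supportive set.

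**Late entry does not touch everyone.** This is also correct. Eltrombopag may be started during antiviral therapy, after consent. A patient who decompensates and survives can still enrol, and historical records may recover the event. A reader might infer that all time before consent is event-free by selection; the protocol does not support that. What cannot be recovered are deaths before consent, and decompensations in patients who never reach prescription and consent.

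**For the target regimen the missed time is at most the 4-week consent window.** That is true if risk is counted from the first combined dose. The plan counts from eltrombopag start, so any lead-in is added.

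**The shifts are smaller than the confidence interval.** The largest, 10% − 7.4% = 2.6 points, is below the stated half-width of 5.8 points at n = 100. But the shift is systematic, and the interval does not reflect it.

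**Conclusion.** The point holds in two limited parts. The inclusion rule and the size and precision figures count all eltrombopag users, whereas the primary aim, the exposure and the analysis preamble concern users on interferon plus a DAA; these passages must be reconciled. And for patients who start eltrombopag before consent, early incidence is biased low because the analysis has no entry time.

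The size of either effect cannot be read from the protocol. The share on the target regimen, the length of the gap, the proportion of patients who have a gap and the shape of the hazard are all assumptions here. Under them, late entry turns a true 10% into between 9.8% and 7.4%.

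It is tempting to read the share of follow-up time lying before entry as the size of the bias. It is not: a 13-week gap is 13/156 = 8% of the three years, yet under a constant hazard it moves the estimate only from 10% to 9.2%. The statement in Section 8.9 is right about users inside the registry. It is incomplete because it says nothing about selection into the registry.

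**What to change.** - **Primary analysis set.** Define it as users who received eltrombopag together with interferon and a DAA, and report all users as a supportive set. Align the wording of Sections 3, 8.1 and 8.5 with Sections 7, 8.3.2 and 8.7.
- **Precision.** Restate the projected number and the half-widths for the restricted set, giving the expected share on interferon plus a DAA.
- **Clock.** Keep eltrombopag start as the time origin. Enter each patient into the risk set at the latest of eltrombopag start, consent and first interferon-plus-DAA dose (delayed entry) in the incidence, Kaplan-Meier and Cox analyses.
- **Pre-entry events.** List those recovered from historical records separately, outside the primary estimate.
- **Section 8.9.** State that including all registry users does not remove selection at registry entry, and that the percentage able to initiate antiviral therapy is conditional on having reached an HCV prescription.

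The cost is a smaller primary set (half-width 0.061 at an assumed 90% share and 0.066 at 75%, against 0.057 for all 105) and small early risk sets, which make the first part of the Kaplan-Meier curve unstable. The consent date must also be in the analysis data; the data list in Section 8.4 does not mention it. No patient's treatment or visit schedule changes.
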